5.6 Data Analysis

Data analysis will be performed by the study biostatistician ([name]) and consultant ([name]) with input from investigator-level study staff (Drs. [name], [name], [name], site PIs). Data analysis will occur at Spectrum Research, Inc. (Tacoma, WA), the University of Washington (Seattle, WA), and Oregon Health & Science University (Portland, OR). Data that is off-site at Spectrum Research, University of Washington, and OHSU for analysis will be coded and will not contain any HIPAA identifiers. See 7.0 *Privacy and Confidentiality* for additional details on data analysis and storage at these locations.

Descriptive Statistics

We will produce descriptive statistics for the recruitment and retention of participants, as well as the frequency of session participation in the intervention group. We will also produce descriptive statistics of patient demographic characteristics, covariates, and outcome measures. For categorical variables, proportions and frequency counts will be calculated. For continuous variables, means, standard deviations, medians, minimum and maximum will be computed. Missing, extreme, and variable distributions will be explored. Missing values patterns will be analyzed.

Statistical analysis of the primary aims

For hypotheses 1a and 1b, we will use Generalized Estimating Equations (GEE) linear regression to investigate mean change over time in MFA-SF. We will model the mean MFA-SF change over time as the outcome, using contrasts $D = MFA-SF[Post\ Intervention] - MFA-SF[baseline]$ and $D = MFA-SF[6\ months] - MFA-SF[baseline]$, versus a treatment indicator, T. The treatment indicator assigns patients T=1 if they receive the VETPALS intervention and T=0 if they receive enhanced usual care. The GEE model will account for intra-cohort level correlation among patients' measurements. The GEE model will provide valid statistical inference if the correlation or variance structure is mis-specified. It does not require normality of model errors. Since the focus of the investigation is to estimate within-patient changes (over time) and the outcome are intra-patient level differences, repeated measures correlation is appropriately accounted for in the model variance estimates. Similarly, we will model the mean PHQ-9 change over time as the outcome, using contrasts $D = PHQ-9[Post\ Intervention] - PHQ-9[baseline]$ and $D = PHQ-9[6\ months] - PHQ-9[baseline]$, versus a treatment indicator, T. The primary analysis will be an as-randomized efficacy assessment comparing the self-management intervention and individual education groups for improvements in depression and physical functioning. The follow-up assessments of participants who do not complete all self-management sessions in the intervention condition will still be included with those who complete the expected course of treatment. This type of analysis provides a more conservative and ecologically valid estimation of treatment effect because it retains all participants and does not screen out individuals who do not tolerate the intervention. Effect size estimates will be obtained. We will assess the randomization assignment by comparing patient-level characteristics (e.g., age, gender, and amputation level) by the treatment indicator and adjust our models with appropriate covariates as necessary.

For hypotheses 2a-e, similar to above, we will fit a GEE model to investigate differences in mean changes in each outcome variable (VAR). We will model the mean change over time as the outcome, using contrasts $\Delta = VAR[Post\ Intervention] - VAR[baseline]$ and $\Delta = VAR[6\ months] - VAR[baseline]$, versus a treatment indicator, T. The treatment indicator assigns patients T=1 if

they receive VETPALS and T=0 if they receive individual education support. The primary analysis will again be a randomized efficacy assessment comparing the self-management intervention and control groups for improvements in self-efficacy, patient activation, and problem solving. The follow-up assessments of participants who do not complete all self-management sessions in the intervention condition will still be included with those who complete the expected course of treatment. This type of analysis provides a more conservative and ecologically valid estimation of treatment effect because it retains all participants and does not screen out individuals who do not tolerate the intervention. Primary analyses will examine changes between baseline and 6-month follow-up scores on outcome measures by treatment group, but we will also examine changes in outcome immediately following the intervention. Effect size estimates will be obtained. Models will be adjusted for covariates as necessary.

For hypothesis 2f, we will produce mean change scores, $\Delta = VAR[6\ months] - VAR[baseline]$, for each outcome measure. We will utilize Pearson product moment correlations to establish associations between changes in our intermediate outcomes and changes in our primary outcomes. This series of analyses is both secondary and exploratory, and is intended to produce preliminary data for a future explanatory model hypothesizing that improvements in self-efficacy, patient activation, and problem solving represent causal mechanisms of self-management intervention that in turn produce improvements in physical and psychosocial outcomes.

Sample Size Justification

Enrollment: Between our 5 sites, we anticipate enrolling approximately 157 subjects per year of recruitment based on previous numbers from the National VA Registry and our already established record of enrollment and follow-up in previous amputation studies conducted by the same core group of investigators. This is a conservative estimate as the inclusion/exclusion criteria for this proposal are more lenient than in our previous studies examining individuals with their first, unilateral amputation. Nonetheless we cautiously project enrollment at 55% of 286, or 157 participants per year. Over the course of 3 years, we expect to accrue 472 enrollees.

Retention: The original PALS self-management study maintained a greater than 90% retention rate. Even assuming a more conservative 75% retention rate for the proposed study, 118 participants per year would be expected to participate and successfully reach their final follow-up. Over the course of 3 years, we expect to retain 354 enrollees. In sum, our sample size estimates are grounded in the specific experience of our team enrolling actual Veterans with limb loss at VA facilities and reflect conservative estimates of recruitment and retention. This is done out of an abundance of caution and we expect that actual rates of recruitment and retention are likely to be higher.

Each primary site intends to recruit one additional secondary site to partner with each primary site (e.g. Seattle partners with Tucson VA). Enrollment, retention, and power analysis sections do not reflect these anticipated partners and do not require them. The purpose of including additional sites is to extend the recruitment and generalizability of the project aims to integrate VETPALS into the VA Amputation System of Care.

Statistical Power

Power estimates are based upon the sample size projections provided in Table 1 below (also in 5.2 Recruitment Methods). Effect size estimates were obtained using the estimates provided in the original PALS study. We anticipated an enrollment of N=51 cohorts in total for the study and

between 6-10 patients per cohort. The treatments, VETPALS and individual education, will be evenly and randomly assigned by cohort. We project between 300 to 500 total patients participating in this study. We investigated changes in each outcome by first computing intra-patient change and accounting for possible intra-cohort level correlation. We assume the baseline and six-month values for the outcomes are highly correlated, with Pearson correlation between 0.6 and 0.8, and the correlation among the change values within a cohort to be modestly correlated, with an intra-class correlation between 0.01 and 0.10. To estimate statistical power to detect the anticipated effect sizes at these proposed sample sizes and correlations, we conducted a series of Monte Carlo simulations based on the analytic framework outlined above. Each of the power calculations were based on 1,000 simulated datasets. Power was computed empirically as the proportion of Wald tests (from correlated data regression estimates from the simulated datasets) that correctly rejected the null hypothesis of no effect, at a five percent alpha level (Type I error rate).

The results indicate that for the modest effect sizes provided, low levels of intra-cohort correlation (ICC) and modest Pearson correlation levels between baseline and six-month measurements (ρ), we will have adequate power to detect differences between the study conditions. To provide two examples, given these conditions we will have power of greater than .8 to detect differences in the primary outcome physical functioning (MFA-SF) (and the additional outcome self-efficacy (MSES).

Anticipated Enrollment

Table 1 (page 25) indicates anticipated enrollment across all 5 sites throughout the 4-year study period. Projections assume a group enrollment rate of 8 ± 2 participants and completion rate of 6 participants per group. We estimate a 50% enrollment rate and expect a 75% retention rate.

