All participants complete a baseline assessment that includes a medical record review, clinical interview, and administration of primary and secondary outcome measures and covariates. Site study coordinators conduct interviews with participants in person or by telephone, whichever is most convenient for the participant. In person interviews take place in a private hospital or clinic room, private room in the Clinical Research Unit, VA hospital library, or VA hospital computer lab. In person interviews may occur individually or in a small group of other study participants. To protect confidentiality and privacy, participants will be seated at separate computers and coordinators will conduct brief cognitive testing with participants individually in a separate room. If the interview is by phone, the study coordinator will ask the participant questions and answers will be marked using an eCRF that is linked to the study database. If the interview is in person, participants can sit at a private computer and respond to questions. The study coordinator is available to answer questions or conduct the interview if the patient does not wish to use the computer. All data are collected using EDC (no paper baseline CRFs) on VA approved and secure laptop and desktop computers. The baseline assessment takes up to one hour to complete.

During the clinical interview, the site study coordinator will collect medical information including amputation date (translated to time in days since original amputation), location, type (initial or revision), and level (e.g. transmetatarsal, transtibial, transfemoral). Although this information was verified and collected during screening, more detailed information, including time (in days) since original date of surgery, is recorded during the baseline assessment.

During the baseline medical record review we will use the Functional Comorbidity Index (FCI), amputation level, previous amputations, and contralateral limb assessment questions. Data will be recorded on eCRFs. A list of the measures used at baseline and follow-up are found in the *assessment measures* section and in Table 2.

Randomization

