Participants randomized to the control group will not have any additional assessments or evaluations to complete. In the event a participant doesn't receive any necessary materials during the individual education support program, a facilitator will mail materials to the participant and will include a return postage-paid addressed envelope if needed. Participants in the control group are offered the VETPALS intervention classes at the end of their 6-month follow-up assessment. Study coordinators will record (yes/no) patients who elect to participate in the intervention classes and will refer patients to the facilitator who will discuss the other program and scheduling in more detail.

Patients who are randomized but unable to begin VETPALS or the Individual Education Support Program

In the event a participant is randomized but cannot begin participating in the assigned intervention, the participant will be given several options. There may be unexpected circumstances (e.g. personal or family illness, change in job status, personal situation) that may prevent a participant from starting the assigned intervention with their cohort as originally planned. VETPALS facilitators will discuss options with the participant.

1. The participant can be included in the same randomized intervention at a later date. The facilitator will wait for the next cohort that is assigned the same intervention and will contact participants to determine if they can participate with the next cohort.
2. If the participant agrees to be included in the next cohort, the facilitator will notify the study coordinator of this change so the study coordinator can include the participant in all subsequent follow-up assessments. The facilitator will only share the participant's study ID number so the coordinator remains blinded to treatment.
3. Participants may be asked to complete a second baseline assessment with the study coordinator. This will be assessed on an individual participant basis and site investigators and the PI will use their discretion when deciding if a second baseline should be completed. Collecting the baseline data again prior to starting the intervention

ensures that the research data reflects the most current responses. Participants who complete a second baseline will receive \$20 for their time and participation.

Periodic medical record review

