Problem Solving will be measured using the 10-item version of the Social Problem-Solving Inventory-Revised (SPSI-R).⁵⁵ This scale assesses two adaptive problem-solving dimensions (positive problem orientation and rational problem-solving) and three dysfunctional dimensions (negative problem orientation, impulsive/careless style, and avoidance style).⁵⁵ Items on the SPSI-R are rated on a five-point Likert-type scale (0, not at all true of me, to 4, extremely true of me) and summed to produce a single total score from 0-40. The SPSI-R has good internal consistency, construct validity, and has been used to assess problem solving in a broad range of populations.⁵⁶

Potential Covariates

The following variables have been established in the literature as correlates of one or both of our primary outcomes. They will be collected primarily to demonstrate the comparability at

baseline of the intervention and control conditions. In instances where randomization does not achieve comparability, outcome analyses will include them as covariates.

Comorbidity will be assessed primarily using the Functional Comorbidity Index (FCI).⁵⁷ The FCI is an 18-item list of diagnoses, each of which is given 1 point if present. The final score of the FCI is the sum of the items. The FCI was designed with physical function as the outcome of interest.⁵⁷ It has been found to have both content and criterion validity. We will also collect a limited number of pre-operative co-morbidity factors and concomitant diseases particularly relevant to amputation outcome (e.g., currently on dialysis - yes/no) from patient interview.

Pain will be measured using questions from the Chronic Pain Grade (CPG) questionnaire.⁵⁸ Participants will be asked to report the intensity and the interference of overall pain as well as pain in each of four different body regions. Response options range from 0 to 10. This assessment of pain location, intensity and impact conforms to established guidelines.⁵⁹ The CPG itself was designed for interview-based studies due to its relatively simple and brief format. The instrument has good internal consistency and reliability.⁵⁸

Complications include stump non-healing, revision to same or higher level, contralateral amputation, and mortality. These will be monitored and collected during the subjects' hospital stay and after discharge by systematically reviewing the subject's medical record every three months as well as during formal follow-up interview at 6 months.

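### Free precision gain: pre-specify each outcome's own baseline as a covariate in the change-score GEE (about 5%–20% less variance at 6 months, given equal SDs and no lasting cohort differences)

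*Combined protocol and SAP*

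**What the plan says.** For hypothesis 1a, section 5.6 (Statistical analysis of the primary aims) states: "We will model the mean MFA-SF change over time as the outcome, using contrasts". The contrasts are post-intervention minus baseline and 6 months minus baseline. They are regressed on a treatment indicator, and the GEE allows for correlation within cohorts. PHQ-9 (1b) and the outcomes of 2a–e follow the same pattern. For 2a–e the 6-month contrast leads: "Primary analyses will examine changes between baseline and 6-month follow-up scores on outcome measures by treatment group".

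Covariates are conditional. After the arms are compared on patient characteristics, the analysts will "adjust our models with appropriate covariates as necessary"; for 2a–e, "Models will be adjusted for covariates as necessary". The Potential Covariates in section 5.5 (comorbidity, pain, complications, social support, cognition, alcohol, smoking) do not include the baseline value of any outcome, and neither does that block of Table 2.

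The baseline values exist for everyone: "All participants complete a baseline assessment that includes a medical record review, clinical interview, and administration of primary and secondary outcome measures and covariates". Section 5.1 adds that the data manager confirms baseline completeness before releasing the allocation.

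Under Statistical Power the plan says: "We assume the baseline and six-month values for the outcomes are highly correlated, with Pearson correlation between 0.6 and 0.8".

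**The concern.** Subtracting baseline fixes its coefficient at 1. When baseline and follow-up correlate below 1 and have equal SDs, that over-corrects: the best coefficient is the correlation itself, here 0.6–0.8. Putting baseline in the model lets the data set the coefficient and removes the excess variance. The plan's own correlation assumption therefore implies that the change-score model gives away precision on both primary outcomes and on 2a–e, using data that will already be in the database. The plan budgets for 25% attrition and has few randomized units (51 cohorts in the power section), so precision that needs no extra participants is worth having.

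**Working it through.** **Inputs from the documents.** Baseline to 6-month correlation ρ = 0.6–0.8; ICC of change within a cohort 0.01–0.10; 6–10 patients per cohort (m); 51 cohorts; 5% alpha, taken as two-sided (all 5.6, Statistical Power). Six completers per group (5.2, Table 1). **Not given:** any SD, the effect size, or the cohort ICC of raw scores.

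**1. The plan's own figure.** Power above .8 for MFA-SF cannot be reproduced without an effect size and SD. I therefore start from an effect that has exactly 80% power on change scores. With 51 cohorts (49 df) its noncentrality is 2.858.

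**2. Patient level, equal SDs.** Var(change) = 2σ²(1−ρ) and the baseline-adjusted variance is σ²(1−ρ²), so the ratio is (1+ρ)/2.
- ρ = 0.6: 0.80, a 20% cut.
- ρ = 0.8: 0.90, a 10% cut.

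The same ratio holds with clustering if baseline reduces the cohort and patient components alike.

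**3. Baseline does not reduce the cohort component.** Ratio = [ICC + (1−ICC)(1+ρ)/(2m)] / [ICC + (1−ICC)/m].
- m = 6, ρ = 0.6, ICC = 0.01: (0.01 + 0.132)/(0.01 + 0.165) = 0.811, a cut of 18.9%.
- m = 6, ρ = 0.8, ICC = 0.10: (0.10 + 0.135)/(0.10 + 0.15) = 0.940, a cut of 6.0%.
- m = 10, ρ = 0.8, ICC = 0.10: (0.10 + 0.081)/(0.10 + 0.09) = 0.953, a cut of 4.7%.

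This formula treats ρ as a within-cohort correlation. If ρ is the overall correlation and baseline has no cohort clustering, the cut is [(1−ρ)/2]/[1+(m−1)ICC]. At ρ = 0.8 and ICC = 0.10 that is 0.10/1.5 = 6.7% (m = 6) and 0.10/1.9 = 5.3% (m = 10). Rounded, the low end is about 6% at 6 per cohort and about 5% at 10. With step 2 as the upper end, the range is 6%–20% or 5%–20%.

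**4. Power.** Dividing 2.858 by √ratio and using 48 df:

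| Ratio | Power |
|---|---|
| 0.80 | 87.9% |
| 0.90 | 83.9% |
| 0.940 | 82.3% |
| 0.953 | 81.8% |

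**5. Unequal SDs.** Let k = month-6 SD / baseline SD and ignore clustering. Ratio = k²(1−ρ²)/(1+k²−2ρk).

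| ρ | k | Ratio |
|---|---|---|
| 0.8 | 0.9 | 0.788 |
| 0.8 | 1.1 | 0.968 |
| 0.8 | 1.25 | 0.5625/0.5625 = 1.000 |
| 0.6 | 0.8 | 0.602 |
| 0.6 | 1.1 | 0.870 |

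**6. Lasting cohort differences.** Suppose cohorts differ in raw score with ICC c, equally at baseline and follow-up. Subtraction removes such a difference completely; a coefficient near ρ removes only part of it. Ratio = 1 − [(1−ρ)/2] × [1−(m−1)c]/[1+(m−1)ICC]. The values of c below are assumptions.
- m = 6: c = 0.15 gives 0.952–0.983. Break-even is c = 1/5 = 0.20.
- m = 10: c = 0.10 gives 0.982–0.995 and c = 0.15 gives 1.018–1.064, a 2%–6% loss. Break-even is c = 1/9 = 0.11.

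If the cohort-mean baseline is added as well, the large-sample cut becomes [(1−ρ)/2] / {[1+(m−1)c][1+(m−1)ICC]}, which cannot be negative. At c = 0.15, m = 10, ρ = 0.6, ICC = 0.01 it is 0.20/(2.35 × 1.09) = 7.8%, in place of the 6.4% loss. Estimating a cohort-level slope from 51 cohorts takes back a little of this. Simulations with 51 cohorts and ICC 0.01, which include that cost, gave ratios of 0.86–0.96 at c = 0.05 and 0.89–0.97 at c = 0.10.

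**The case against.** The best defence is that the plan chose one of two valid estimators. Change from baseline is what the hypotheses in section 4.0 are about, it is unbiased under randomization, and the plan already claims power above .8. All of this stands. A reader might infer that the change-score model is biased or that the trial is underpowered. The documents support neither: the stated power can be neither confirmed nor refuted, and the adjusted model may keep change as its outcome.

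A reader might also infer that the baseline scores go unused. They do not, since baseline is subtracted in every contrast. What is missing is their second use as a covariate.

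It can be said that the gain is not guaranteed. That is right: steps 5 and 6 show where it vanishes or reverses. Cohorts fill consecutively within sites (5.1), so lasting differences between them cannot be excluded. However, the reversal needs large analysed cohorts. At the 6 completers the plan expects, c would have to exceed 0.20.

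Finally, adjusting as necessary may already allow a baseline covariate. It does, but only after looking at the data, and no listed covariate is an outcome baseline.

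Two nearby matters should not be read into this point. One is the imbalance trigger ("In instances where randomization does not achieve comparability, outcome analyses will include them as covariates"), which gives no threshold and is mainly missing detail. The other is the repeat baseline for late starters, where "site investigators and the PI will use their discretion when deciding if a second baseline should be completed". Those participants join a later cohort, so either choice of baseline for their change score has a cost. Both deserve their own discussion; neither supports the efficiency claim.

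**Conclusion.** The point holds as an efficiency improvement that should be made, not as an error. Baseline is not a pre-specified covariate in any of the GEE models for 1a, 1b and 2a–e. Adding it is expected to cut the variance of the 6-month treatment estimate by about 6%–20% at 6 completers per cohort (about 5%–20% over 6–10), which takes 80% power to about 82%–88%.

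This rests on the plan's ρ and ICC ranges and on two assumptions that the documents cannot confirm: equal SDs at baseline and month 6, and no lasting cohort differences in raw score. The 5% end also assumes 10 analysed patients per cohort, more than the plan expects. The plan gives ρ only for six months, so the gain at the post-intervention contrast is unknown.

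**What to change.** In section 5.6, for hypotheses 1a, 1b and 2a–e, name the pre-randomization value of the same outcome as a fixed covariate in the cohort-clustered GEE, whatever the observed balance. The outcome can remain change from baseline: with the same baseline on both sides, the treatment estimate equals that from modelling the follow-up score with baseline as covariate. Adding the cohort-mean baseline is a reasonable guard against lasting cohort differences and is advisable if analysed cohorts may be near 10.

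Cost: a few sentences and no new data. The baseline term uses 1 df, which with 51 cohorts moves the detectable-effect multiplier from 2.858 to 2.859. The cohort-mean term would use one more.

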Enrolled participants are assigned on a rolling basis into successive cohorts of 8±2 individuals at each participating site. Each time 8±2 participants are enrolled, that cohort will be randomized 1:1 to receive either the VETPALS intervention or individual education support program (control condition). We will ensure that participants will not have completed a PALS program prior to study participation and will not be part of an existing PALS group during their study participation. Randomization will occur through an email exchange between the study sites (VETPALS facilitator or site PI) and the data manager at Spectrum Research. The data manager will maintain a randomization table that is stored locally on a server at Spectrum Research. When a cohort is ready for randomization, the facilitator or site PI will send an email to the data manager stating that a group of participants is ready for randomization. The email will also include a list of study ID numbers but will not contain any information that could identify participants. Within 12-24 hours of receiving the email, the data manager will verify the list of study IDs in the database to ensure all baseline assessments are complete, and then will obtain random assignment by accessing the randomization table. The data manager will respond via email to the facilitator or site PI with a value of 0 or 1 (0=individual education support program, 1=VETPALS). Both parties will retain a copy of the email for reference. The data manager will record the treatment assignment for the group in the randomization table, and the facilitator or site PI will record the treatment assignment in the randomization log. This method will ensure that treatment allocation is concealed during the recruitment of each cohort. A balanced number of groups will be randomly assigned to each site based on the projected enrollment at that site, which is a common randomization schedule used in group-based interventions. The randomization schedule and algorithm will not be shared with local sites to maintain concealment of treatment allocation. Additionally, the data manager will record a value of 0 or 1 to each study ID in the database which is linked to the study ID assigned at enrollment. Clinical research staff at each location (applicable investigators and VETPALS facilitators) will receive the treatment allocation and randomization ID in order to proceed with the treatment, intervention or control. Site study coordinators who conduct the baseline and follow-up assessments are blind to treatment.

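### Cohorts are allocated in balance by site, but the GEE models omit site; if sites differ in change scores, standard errors are conservative and some precision is forgone

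*Combined protocol and SAP*

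**What the plan says.** **Allocation.** Section 5.1 (Study Overview) makes the cohort the unit of randomisation: "that cohort will be randomized 1:1 to receive either the VETPALS intervention or individual education support program". On site it adds: "A balanced number of groups will be randomly assigned to each site based on the projected enrollment at that site". The natural reading is that the two arms are balanced within each site, although the plan never uses the word stratified.

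**Model.** Section 5.6 models each change score "versus a treatment indicator, T. The treatment indicator assigns patients T=1 if they receive the VETPALS intervention". The only clustering it handles is by cohort: "The GEE model will account for intra-cohort level correlation". The models for hypotheses 2a-e follow the same form.

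**Covariates.** For the primary outcomes, 5.6 says "We will assess the randomization assignment by comparing patient-level characteristics", with age, gender and amputation level as examples, and then that the team will "adjust our models with appropriate covariates as necessary". For the secondary outcomes it says only "Models will be adjusted for covariates as necessary". The Potential Covariates list in 5.5 covers comorbidity, pain, complications, social support, cognition, alcohol and smoking. It does not include site, and its items enter only where randomisation has not made the arms comparable.

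**The concern.** When allocation is balanced within site, differences between sites in mean change largely cancel from the treatment contrast. A model without site still counts those differences as variation between cohorts, so the reported standard error is larger than the true variability of the estimate.

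Sites could plausibly differ. Each has its own coordinator, facilitator and peer co-leader, one has a second facilitator who is a psychologist, and the plan itself expects local factors to affect delivery and retention.

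The covariate rule is unlikely to repair this. It responds to imbalance between arms, and a site-balanced schedule tends to prevent that imbalance for site. Using the clause to add site later would also leave a choice about the primary model until after the data are seen. At stake are the width of the confidence intervals and some power for both primary outcomes.

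**Working it through.** **1. The plan's own figures.** Table 1 implies 12 + 12 + 15 + 12 + 8 = 59 cohorts. Then 59 × 8 = 472 enrolled and 59 × 6 = 354 retained, which is 0.75 × 472; all match. The Statistical Power text gives 51 cohorts, a separate discrepancy. The stated power above 0.8 for MFA-SF cannot be reproduced, because no effect size or SD is given.

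**2. Inputs.** From the plan: 6 completers per cohort (Table 1), intra-cohort correlation of change 0.01-0.10 and alpha 5% (Statistical Power). Assumed: a two-sided test, and the share *s* of the variance of change that lies between sites. The rest of the intra-cohort correlation, *c*, is between cohorts within site.

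**3. Standard error.** Variance of a cohort mean, total variance of change set to 1:

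- site removed: V = c + (1 − s − c)/6
- as seen by the model without site: V + k·s
- SE ratio: √[(V + k·s)/V]

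The simple form takes k = 1. With only five sites, the expected spread seen in the sample is smaller: k = 1 − Σn²/N² = 1 − (3 × 144 + 225 + 64)/59² = 1 − 721/3481 = 0.793.

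**4. Size and power.** Under exact balance, the size of the unadjusted test is 2[1 − Φ(1.96 × ratio)]. If the site-adjusted analysis has power 0.80, the unadjusted power is Φ(2.802 − 1.96 × ratio).

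| s, c | V | SE ratio, k = 1 | SE ratio, k = 0.793 | Size (k = 1; 0.793) | Power (k = 1; 0.793) |
|---|---|---|---|---|---|
| 0, any | – | 1.000 | 1.000 | 5.0%; 5.0% | 0.80; 0.80 |
| 0.01, 0.04 | 0.198 | 1.025 | 1.020 | 4.5%; 4.6% | 0.79; 0.79 |
| 0.02, 0.03 | 0.188 | 1.052 | 1.041 | 3.9%; 4.1% | 0.77; 0.78 |
| 0.05, 0.05 | 0.200 | 1.118 | 1.095 | 2.8%; 3.2% | 0.73; 0.74 |

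At the bottom of the plan's range (total 0.01, half of it site), V = 0.005 + 0.99/6 = 0.170 and the ratio with k = 1 is √(0.175/0.170) = 1.015.

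**5. Simulation.** Both runs used 59 cohorts split 12/12/15/12/8.

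- With a small-sample-corrected test and site shares 0, 0.01, 0.02 and 0.05, the unadjusted SE was 0%, 2%, 4% and 10% larger than the adjusted one. Size was 4.8%, 4.6%, 4.1% and 3.2% unadjusted, against 4.6-5.1% adjusted. Power was about 0, 1, 2 and 6 points lower.
- A second run (3,000 trials per setting, effect 0.32 SD of change, c = 0.03, 4-8 completers per cohort) gave power without and with site of 80.1% and 80.2% at share 0, 78.2% and 79.4% at 0.01, 77.9% and 81.4% at 0.03, and 75.9% and 81.3% at 0.05. Monte Carlo error is about 0.8 points.

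**6. Incomplete balance.** Houston's 15 cohorts can split only 8/7. At site share 0.05 this adds noise with SD about 0.006 against an SE of about 0.116, and (0.006/0.116)² = 0.27% of the variance. When sites were simulated as stopping at 50-100% of projection, the unadjusted estimate stayed within 0.004 SD of the truth on average. Its true spread at share 0.05 was about 1.5% above the adjusted one (0.1329 against 0.1309).

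**7. Test size once site is added.** With an uncorrected sandwich variance and a normal reference, the site-adjusted test ran at about 6.5-7%. In the second run of step 5, which scaled the variance for the number of model terms but kept the normal reference, it ran at 5.1-6.3%.

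**The case against.** **The size of the effect is assumed.** No section gives between-site variance in change. Stable site differences in level cancel in a change score. Facilitator differences act mainly in the VETPALS arm, so part of any site variation would be site-by-treatment variation, which a site main effect does not properly remove. This stands, and it is why the result is given as a range that starts at zero.

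**The stated power may be intact.** A reader might infer that the trial falls below its stated power. The documents do not support that. Section 5.6 simulated power under its own framework, which is the model without site. If that model has 0.80 at the stated intra-cohort correlation, within-site balance raises its actual power to Φ(0.842 × ratio): 0.81 at ratio 1.052 and 0.83 at 1.118. The site-adjusted analysis would have Φ(2.802 × ratio − 1.96): 0.84 and 0.88. On that footing the loss is a forgone gain of about 3-5 points. This stands.

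**There is no bias.** A reader might also infer that uneven numbers within a site, or the undecided Year 4 at Minneapolis, carry site differences into the estimate systematically. They add chance noise only, and step 6 shows that it is small.

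**Balance within site is inferred.** Section 5.6 says only that treatments are assigned evenly by cohort, and section 8.0 describes a random distribution with no visible pattern. If arms are not balanced within site, the unadjusted SE is not conservative; site differences instead add real variability to the estimate. A site term helps in that case too, so the remedy does not turn on the reading.

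**The covariate clause could admit site.** Its characteristics are only examples, so site is unspecified rather than excluded. That is correct, but nothing commits the analysis to site, and the trigger points the other way.

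**Conclusion.** The point holds as a low-cost improvement in precision. The models in 5.6 do not reflect the site balance that 5.1 builds into the allocation, and the covariate rule would tend not to add site. If sites differ in change, the unadjusted SE is about 2% too large at a site share of 0.01, 4-5% at 0.02 and 10-12% at 0.05. Power is roughly 1, 2-4 and 5-7 points below that of a site-adjusted analysis. If sites do not differ, nothing is lost.

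These figures rest on the assumed shares, 6 completers per cohort, 59 cohorts in the simulations and near-complete balance of arms within site.

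The error is conservative: omitting site does not inflate type I error. Nor should a reader conclude that the planned test necessarily runs below 5%. An uncorrected sandwich test with this many cohorts is itself somewhat liberal, and at small site shares the two effects roughly offset.

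**What to change.** State in 5.6 that every GEE for hypotheses 1a, 1b and 2a-e includes site as a five-level fixed factor, with partner-site participants coded to their primary site, regardless of any imbalance check. Keep cohort as the cluster. In the same place, specify a small-sample-corrected sandwich variance with a t reference. Without that correction, adding site would move the test to about 6.5-7%, and part of the apparent power gain would be extra type I error.

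The cost is a short addition to 5.6 and 4 cohort-level degrees of freedom out of about 57 (59 cohorts less 2 model terms). If sites do not differ and balance is complete, power is essentially unchanged (80.2% with site, 80.1% without). If they do not differ and sites stop well short of projection, the simulated cost was about one point (67.3% against 68.4%), close to simulation error.
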